6.6 Breaking the Blind

At the initiation of the study, the study site will be instructed on the method for breaking the blind. The method will be an electronic process.

The electronic system will be programmed with blind-breaking instructions. In case of an emergency, the investigator has the sole responsibility for determining if unblinding of a subject's product assignment is warranted. Subject safety must always be the first consideration in making such a determination. If the investigator decides that unblinding is warranted, the investigator should make every effort to contact the sponsor prior to unblinding a subject's product assignment unless this could delay emergency treatment of the subject.

If a subject's product assignment is unblinded, the sponsor must be notified within 24 hours after breaking the blind. The date and reason that the blind was broken must be recorded in the source documentation and case report form, as applicable.

Any AE associated with breaking the blind must be recorded and reported as specified in this protocol. The study site may also be required to inform the Institutional Review Board (IRB) if the blind is broken.

6.7 Compliance

To facilitate subject compliance with product usage requirements:

- First use of their assigned study dentifrice will be carried out under supervision at the study site at the end of the baseline visit (Visit 2); study staff will demonstrate the correct amount of dentifrice to dispense and how to use the timer to ensure a 2-minute brushing time. A further supervised brushing will be carried out at the study site at the end of Week 4 procedures (Visit 3).
- Subjects will be provided with a diary at baseline (Visit 2) and Week 4 (Visit 3) to record each completed brushing with study product.
- Subjects will attend each study visit with all tubes of dentifrice provided (used and unused) for a visual check of product usage, and with their completed diary for review by study staff. Any suspected over or under use, the number of any missed or additional brushings will be documented as deviations in the CRF; subjects will be re-instructed in the correct use of product and diary completion, as required
- Subjects will also use the diary to note any issues with their study product, any oral problems, illnesses and new medications/ treatments. Details relevant to safety or efficacy should be reviewed by the investigator (or suitably qualified designee) and transcribed to the CRF, as appropriate; AEs must be documented in the CRF.

The number of any missed or additional applications or doses will be captured as protocol deviations. Subjects will be re-instructed in the correct usage requirements and diary completion as needed.

A record of the number of dentifrice tubes dispensed to and taken by each subject must be maintained and reconciled with study intervention and compliance records. Intervention start and stop dates, including dates for intervention delays and/or dose reductions will also be recorded in the CRF.

6.8 Concomitant Medication/Treatment(s)

Any medications, treatments or vaccine (including over-the-counter or prescription medicines, vitamins, and/or herbal supplements) taken during the study, from signing the informed consent, must be recorded in the CRF with indication, reason for use, unit dose, daily dose, and start and stop dates of administration. All subjects will be questioned about medications/treatments at each site visit.

Medication/treatments taken 28 days prior to signing the informed consent form and until first study product application will be documented as a prior medication/treatment. Medications/treatments taken after first study product application will be documented as concomitant medication/treatments.

7 DISCONTINUATION OF STUDY INTERVENTION AND SUBJECT DISCONTINUATION/WITHDRAWAL

7.1 Subject Discontinuation/Withdrawal

A subject may withdraw from the study at any time at their own request or may be withdrawn at any time at the discretion of the investigator or sponsor for safety, behavioral reasons, or the inability of the subject to comply with the protocol-required schedule of study visits or procedures.

The following circumstances require discontinuation of study product and/or premature subject withdrawal:

- Protocol violation that may impact the subject's safety
- Withdrawal of informed consent
- Subject lost to follow-up
- Unblinding of the subject
- Pregnancy

If a subject is discontinued or prematurely withdraws from the study, the reason(s) for discontinuation or withdrawal and the associated date must be documented in the relevant section(s) of the CRF.

7.2 Lost to Follow up

If a subject fails to return to the site for a required study visit, the site must attempt to contact the subject and reschedule the missed visit as soon as possible and counsel the subject on the importance of maintaining the assigned visit schedule and ascertain whether the subject wishes to and/or should continue in the study.

A subject will be considered lost to follow up if they repeatedly fail to return for scheduled visits and is unable to be contacted by the study site. Before a subject is deemed lost to follow up, the investigator or designee must make every effort to regain contact with the subject (where possible, 3 telephone calls and, if necessary, a certified letter to the subject's last known mailing address or local equivalent methods). These contact attempts should be documented. If contact is made with the subject, the investigator should inquire about the reason for withdrawal, request that the subject return all products provided and, if appropriate, request that the subject return for a final visit and follow-up with the subject regarding any unresolved adverse events (AEs).

Final safety assessments may be carried out when the subject returns to the study site, at the investigator's discretion, which could include an oral examination.

Should the subject continue to be unreachable, they will be considered to have withdrawn from the study and lost to follow up.

Lack of completion of all or any of the early termination procedures will not be viewed as protocol deviations so long as the subject's safety was preserved.

If the subject withdraws from the study and withdraws consent for disclosure of future information, no further evaluations should be performed, and no additional data should be collected. The sponsor may retain and continue to use any data collected before such withdrawal of consent.

8 STUDY PROCEDURES

This section lists the procedures to be completed at each planned study visit. The timing of each procedure is listed in the Schedule of Activities section.

Adherence to the study design requirements, including all procedures is essential and required for study conduct.

8.1 Visit 1/Screening

Screening procedures will be conducted by the Investigator, or suitably qualified designee.

The following screening procedures will be completed, in the following order (wherever possible), and the findings recorded in the CRF:

1. Informed Consent
2. Demographics
3. Review of medical history (including smoking/tobacco use status) and prior/concomitant medication/treatment
4. Full OST and OHT examinations
5. Review of the inclusion/exclusion criteria
6. Subject eligibility

8.1.1 Screening Procedures

8.1.1.1 Informed Consent

The investigator, or designee, must obtain informed consent from each subject participating in this study after adequate explanation of the aims, methods, objectives, and potential hazards of the study. An ingredients listing for the study dentifrices will be provided to each subject during the consent process to enable them to confirm they are not aware of any allergy or hypersensitivity to any of the ingredients listed. Two copies of the informed consent form (ICF) will be signed and dated by the subject, the subject will retain one copy and the other will be kept at site.

The investigator, or designee, must also explain to the subjects that they are completely free to refuse to enter the study or to withdraw from it at any time. Appropriate forms for documenting a signed and dated consent will be provided by either the investigator or by the sponsor.

The investigator, or designee, should sign and date each copy of the ICF to confirm that the consent process was completed correctly after the subject has signed.

The time the subject signed the ICF will be captured as this is the point from which all AEs will be captured. The date and time of consent will be recorded in the CRF.

If, during a subject's participation in the study, any new information becomes available that may affect the subject's willingness to participate in the study, each ongoing subject should receive a copy of this new information and be re-consented into the study. Each subject should be provided with a copy of the signed and dated amended consent form. The date of re-consent will be recorded on the CRF.

After signing the ICF, subjects will undergo the screening assessments to confirm that they meet all the inclusion criteria and none of the exclusion criteria. If the subject is confirmed eligible by the investigator (or designee) to participate in the study the subject is considered enrolled in the study.

8.1.1.2 Demographics

The following demographic information will be recorded in the CRF: year of birth, gender and race. Ethnicity and race of subjects will be recorded in accordance with FDA Guidance ([US FDA, 2005](#)).

8.1.1.3 Medical History and Prior Medication/Treatment

Details of relevant medical and surgical history (in the last year), including allergies or drug sensitivity, will be documented in the CRF.

Prior medications/treatments, including prescription and non-prescription drugs, dietary supplements and herbal remedies, taken in the last 28 days and prior to signing the informed consent form, will be documented in the CRF.

8.1.1.4 Oral Examinations

Following review of the oral care products the subject is currently using (subject-reported product names) to confirm they do not contain any ingredients that could interfere with study outcomes, the clinical examiner(s) will perform the following examinations/assessments.

- OST examination.
- OHT examination.
- Confirm eligibility of the anterior teeth against the dentition exclusions described in [Section 5.3](#).

Oral examinations/assessments should only be performed by suitably qualified examiner(s) as described in [Section 5.8](#).

To facilitate subject flow, clinical assessments may be recorded on a paper source document and later transcribed into the CRF.

8.1.1.5 Inclusion/Exclusion Criteria

Inclusion and exclusion criteria information will be documented in the CRF.

8.1.1.6 Subject Eligibility

The investigator and/or medically qualified designee will review the inclusion/exclusion criteria, medical history, prior and current medications/treatments and the findings of the oral examinations to confirm subject eligibility to participate in the clinical trial. This will be documented in the CRF.

To prepare for study participation, subjects will be instructed in the [Lifestyle Guidelines](#) and any [Concomitant Medication/Treatment\(s\)](#) requirements of the protocol.

8.2 Study Period

8.2.1 Visit 2/Day 0 - Baseline

Procedures will be conducted by the Investigator, or suitably qualified designee.

Subjects will undergo, in the following order (wherever possible).

1. MLSI is assessed on the facial surfaces of the six maxillary anterior teeth and six mandibular anterior teeth (tooth numbers 6-11 and 22-27), and the lingual surfaces of the six mandibular anterior teeth (tooth numbers 22-27), including a repeat assessment if required. At the examiner's discretion, the examiner may use floss and/or a wetted toothbrush to remove debris from the teeth prior to the assessment if required.
2. Clinical assessment of tooth shade is performed on the facial surfaces of the central and lateral maxillary incisors (tooth numbers 7-10) through use of the VITA Bleachedguide 3D-MASTER instrument including a repeat assessment if required.
3. Tooth color is assessed through use of the VITA EasyShade instrument.
4. Review of the inclusion/exclusion criteria.
5. Subject eligibility assessed. Subjects who do not meet the criteria for participation will be discontinued.
6. Qualifying subjects will be stratified and randomized to treatment groups.
7. Study products will be dispensed, including sundry items, and diary.
8. Instruct subject in product usage requirements/diary completion and demonstrate dispensing ribbon of dentifrice on to toothbrush head; supervise first brushing and first diary entry.
9. AEs and incidents recorded.

Randomized subjects will be appointed to attend the study site for their Week 4 assessments and reminded of the Lifestyle Guidelines and to bring their study product and completed diary with them to the next visit.

To facilitate subject flow, clinical and instrumental assessments may be recorded on a paper source document and later transcribed into the CRF.

8.2.2 Visit 3/Week 4 (Day 28 ± 3)

Procedures will be conducted by the Investigator, or suitably qualified designee.

Subjects will undergo, in the following order (wherever possible), and findings recorded in the CRF:

1. Changes in concomitant medication or non-drug treatments/procedures will be documented.
2. Spontaneous reporting of adverse events and those elicited by asking subjects to respond to a non-leading question such as "How do you feel?" will be assessed.
3. Subject will return study products and diary for visual inspection to evaluate product compliance and adherence to protocol. Subject continuance in the study confirmed.
4. Subject undergoes an OST examination.

5. MLSI is assessed on the facial surfaces of the six maxillary anterior teeth and six mandibular anterior teeth (tooth numbers 6-11 and 22-27), and the lingual surfaces of the six mandibular anterior teeth (tooth numbers 22-27), including a repeat assessment if required. At the examiner's discretion, the examiner may use floss and/or a wetted toothbrush to remove debris from the teeth prior to the assessment if required.
6. Clinical assessment of tooth shade is performed on the facial surfaces of the central and lateral maxillary incisors (tooth numbers 7-10) through use of the VITA Bleachedguide 3D-MASTER instrument including a repeat assessment if required.
7. Tooth color is assessed through use of the VITA EasyShade instrument.
8. Resupply of allocated study products will be dispensed, including sundry items, and diary.
9. Re-instruct subject in product usage requirements/diary completion; supervise on-site brushing and diary entry.
10. AEs and incidents recorded.

Subjects will be appointed to attend the study site for their Week 8 assessments and reminded of the Lifestyle Guidelines and to bring their study product and completed diary with them to the next visit.

To facilitate subject flow, clinical and instrumental assessments may be recorded on a paper source document and later transcribed into the CRF.

8.2.3 Visit 4 /Week 8 (Day 56 ± 3)

Procedures will be conducted by the Investigator, or suitably qualified designee.

Subjects will undergo, in the following order (wherever possible).

1. Changes in concomitant medication and/or non-drug treatments/procedures will be documented.
2. Spontaneous reporting of adverse events and those elicited by asking subjects to respond to a non-leading question such as "How do you feel?" will be assessed.
3. Subject will return study products and diary for visual inspection to evaluate product compliance and adherence to protocol. Subject continuance in the study confirmed.
4. Subject undergoes OST and OHT examinations.
5. MLSI is assessed on the facial surfaces of the six maxillary anterior teeth and six mandibular anterior teeth (tooth numbers 6-11 and 22-27), and the lingual surfaces of the six mandibular anterior teeth (tooth numbers 22-27), including a repeat assessment if required. At the examiner's discretion, the examiner may use floss and/or a wetted toothbrush to remove debris from the teeth prior to the assessment if required.
6. Clinical assessment of tooth shade is performed on the facial surfaces of the central and lateral maxillary incisors (tooth numbers 7-10) through use of the VITA Bleachedguide 3D-MASTER instrument including a repeat assessment if required.
7. Tooth color is assessed through use of the VITA EasyShade instrument.
8. AEs and incidents recorded.
9. Study conclusion.

To facilitate subject flow, clinical and instrumental assessments may be recorded on a paper source document and later transcribed into the CRF.

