5.5.5 Medication and Treatment Restrictions

- **Visits 1-4:** Subjects will be asked to delay elective dental treatment (for example, dental prophylaxis) for the duration of the study. They will be required to inform site staff of any emergency treatment they receive during the study.
- **Visits 3 & 4:** Subjects will be asked to inform site staff of changes to their medications/treatments for the duration of the study. Should a subject commence a course of medication which, in the opinion of the investigator or medically qualified designee, could impact study outcomes, the subject may be withdrawn.

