12.2 Populations for Analysis

12.2.1 Definitions of Analysis Populations

The Safety population will include all randomized subjects who complete at least one use of study product. This population will be based on the study product the subject received. All assessments of safety will be based on this analysis population.

The modified Intent-To-Treat (mITT) population will include all randomized subjects who complete at least one use of study product and have at least one post baseline efficacy assessment. This population will be based on the study product to which the subject was randomized. All assessments of efficacy will be primarily based on this analysis population.

The per protocol (PP) population is defined as all subjects in the mITT population who have at least one assessment of efficacy considered unaffected by protocol violations.

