4.1.2 Protocol Deviations

Protocol deviations will be tracked by the study team throughout the conduct of the study. Data will be reviewed prior to unblinding and closure of the database to ensure all important deviations are captured and categorised. Subjects with important protocol deviations liable to influence the efficacy outcomes will have affected data excluded from the PP analyses. Subjects may also be identified as having important protocol deviations not leading to exclusion of data from the PP analyses.

Important deviations of the protocol procedures may include, but will not necessarily be limited to the following:

- Consent procedures
- Inclusion/Exclusion criteria
- Study procedures
- Non-compliance with product administration
- Inadmissible concomitant medication

The specific details of the important protocol deviations will be listed in Protocol Deviation Management Plan and assessment process will be specified in the Blind Data Review Plan and subjects with important protocol deviations will be identified at the BDRM.

The number and percentage of subjects with at least one important protocol deviation, at least one important protocol deviation not leading to exclusion of data from PP analyses (overall and by each deviation reason) and at least one important protocol deviation leading to exclusion of

data from the PP analyses (overall and by each deviation reason) will be presented by study product (Table 14.1.2) and listed in Listing 16.2.2.1.

All protocol deviations collected on the protocol deviation case report form page will be listed in Listing 16.2.2.2. The listing will present date of deviation, type of deviation, and deviation description.

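### At Weeks 4 and 8 the continuance check comes before the stain and shade scoring, so a discretionary withdrawal of an attending subject can bring outcome-related selection into the mITT analysis

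*Protocol*

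**What the plan says.** **Visit order.** Protocol 8.2.3 (Week 8) opens with "Subjects will undergo, in the following order (wherever possible") and then lists: medication changes (1), adverse events (2), product and diary return (3), oral examinations (4), MLSI (5), VITA shade (6), EasyShade (7). Step 3 is "Subject will return study products and diary for visual inspection to evaluate product compliance and adherence to protocol. Subject continuance in the study confirmed". Protocol 8.2.2 (Week 4) has the same steps 1 to 3, including "Subject continuance in the study confirmed", with the scoring again at 5 to 7. At Week 8 only safety recording and study conclusion come after the scoring.

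**Withdrawal.** Protocol 5.5.5, in an item labelled for Visits 3 and 4, says that if a subject starts a medication that in the investigator's opinion "could impact study outcomes, the subject may be withdrawn". Protocol 7.1 adds that a subject "may be withdrawn at any time at the discretion of the investigator or sponsor for safety, behavioral reasons", or for inability to comply with required visits or procedures.

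**Missed brushings.** Protocol 6.7 and 8.2.4.1 treat missed or extra brushings as deviations, and 6.7 adds re-instruction.

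**Analysis.** Protocol 12.2.1 requires mITT subjects to "have at least one post baseline efficacy assessment". SAP 4.1.2 names product non-compliance and inadmissible concomitant medication as possible important deviations and says: "Subjects with important protocol deviations liable to influence the efficacy outcomes will have affected data excluded from the PP analyses". Such subjects are identified at the blinded data review meeting. SAP 4.4.4 uses data up to discontinuation without imputation, relies on missing at random, and leaves sensitivity analyses optional.

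**The concern.** The continuance decision is taken after the site has seen the tubes, the diary and the medication changes, and before the examiner has scored the teeth. At Week 8 no further product use follows, so a negative decision there saves nothing for the trial and can cost the Week 8 primary value of a subject who is in the clinic. At Week 4 it can leave a randomized subject with no post-baseline efficacy value, and so outside mITT.

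The medication ground in 5.5.5 is defined by its possible effect on study outcomes. Removal on that ground is therefore likely to be related to what would have been measured. The SAP's route for the same events keeps the subject in mITT and lets a blinded meeting decide on PP exclusion. The visit order opens a second, earlier route that is discretionary and reaches the primary population.

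The mixed model repairs this only in part. Under missing at random, a withdrawn subject is taken to follow others on the same product with the same smoking status and similar observed scores. For a medication started after Week 4, the Week 4 score carries no trace of it.

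**Working it through.** **1. The passages side by side**

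| Event found at the visit | Visit-level provisions | Analysis route in the SAP |
|---|---|---|
| New medication that could affect outcomes | May be withdrawn (5.5.5), with the continuance item before scoring | Possible important deviation; affected data out of PP only, after blinded review |
| Missed or extra brushings | Deviation, with re-instruction (6.7, 8.2.4.1); only the general discretion in 7.1 could go further | The same |
| Withdrawn at Week 4, step 3 | No post-baseline score | Not in mITT |
| Withdrawn at Week 8, step 3, with Week 4 scored | Week 8 score missing | In mITT; contributes Week 4 through the MMRM |

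No passage requires the due scoring to be completed before a withdrawal is recorded.

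**2. The plan's own figures**

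Inputs from Protocol Table 12-1: 90 per arm; MLSI difference 0.3, SD 0.4; VITA difference 1, SD 2. A two-sample t-test at two-sided 5% gives:
- VITA, effect size 1/2 = 0.5: power 91.6% (plan: 91.5%).
- MLSI, effect size 0.3/0.4 = 0.75: power 99.9% (plan: 99.8%).
- Randomized per arm: 90/0.9 = 100, as planned.

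The sample size contains no error on this point.

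**3. Illustrative size of the selection**

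Assumption, not in the documents: a share p of an Experimental arm is removed at step 3 and would have changed as the Reference arm does. The retained subjects show the planned difference D, and the estimate rests on them. The difference over all randomized subjects is then D × (1 − p), and the overstatement is 1/(1 − p) − 1.

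| p | VITA, D = 1.0 | MLSI, D = 0.30 | Overstatement |
|---|---|---|---|
| 2% | 0.98 | 0.294 | 2.0% |
| 5% | 0.95 | 0.285 | 5.3% |
| 10% | 0.90 | 0.270 | 11.1% |

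Week 4 data in the MMRM would reduce this to the extent that missing at random holds.

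**4. The primary within-product test**

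Table 12-1 assumes an MLSI change of 0.6 with SD 0.4, so a Reference-like change is 0.6 − 0.3 = 0.3. Over all randomized subjects the change is 0.6 − 0.3p: 0.594, 0.585 and 0.570 for p = 2%, 5% and 10%. Even 0.570 is 0.570/(0.4/√90) = 13.5 standard errors from zero. If removed subjects fell short of their own arm's mean by the same amount in every arm, the effect would cancel between products but not in this within-product change.

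**5. Loss of information**

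If a further 2%, 5% or 10% of the 90 were lost beyond the planned dropout (88.2, 85.5 or 81 per arm), VITA power would be 91.0%, 90.2% or 88.5%. MLSI between-product power would stay at 99.7% or more. Losses inside the 10% allowance cost no planned power.

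**The case against.** The case against a serious defect is substantial, and most of it stands.

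- **Non-compliance.** A reader might infer that subjects are to be withdrawn for missed brushings. The specific rules say otherwise: deviation and re-instruction, with no compliance threshold. The general discretion for behavioral reasons remains, but the medication ground is the stronger one.
- **mITT becoming per-protocol.** A reader might infer that the visit order turns the primary analysis into a discretionary per-protocol one. The documents do not support this. Deviators who are scored stay in mITT, and a subject withdrawn at Week 8 with a Week 4 score stays too. Only removal at Week 4 before scoring takes a subject out.
- **Unblinded removal.** A reader might infer that the decision is made with knowledge of the product, because the trial is labelled examiner-blind. Protocol 6.5 also blinds site staff who may influence outcomes, and 6.1.2 has all tubes overwrapped. Removal that depends on the arm is not shown.
- **Completing assessments.** Protocol 9 asks for every effort to complete required assessments and makes a missed one a deviation to be reported to the sponsor. The visit order is to be followed only where possible.
- **Purpose of the item.** Step 3 follows the medication and adverse-event review, so it is not only a compliance filter.

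What remains is a gap. The general wish to complete assessments does not say whether scoring or a withdrawal decision comes first, and the listed order puts the decision first.

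**Conclusion.** The point holds as a possibility that the text leaves open. It does not describe what the plan directs. An attending subject can be withdrawn just before scoring, at the cost of the primary value at Week 8 or of mITT membership at Week 4, outside the blinded review that the SAP provides for the same deviations.

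The size is unknown because no withdrawal rate is given. An overstatement of about 2% to 11% between products rests on the assumed 2% to 10% removal of Reference-like responders from an Experimental arm, with no recovery through Week 4 data. The risk is to estimates more than to significance, and the within-product MLSI conclusion is not in realistic danger. The change is still worth making because it costs almost nothing and protects data that the visit exists to collect.

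**What to change.** 1. In Protocol 8.2.2 and 8.2.3, place MLSI, VITA shade and EasyShade before the continuance item. At Visit 4 the item could instead be dropped, there and in the Schedule of Activities, since no treatment follows.
2. State that a randomized subject who attends completes the due efficacy assessments before any continuance decision is recorded, unless the subject declines or safety prevents it. The deviation is recorded, and PP exclusion is left to the blinded data review under SAP 4.1.2.
3. Reconcile Protocol 5.5.5, 6.7, 7.1, 8.2.2 and 8.2.3 with SAP 4.1.2 on how non-compliance and new medication are handled. No view is taken here on which withdrawal rule is right.

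The cost is protocol wording. The subject is already in the clinic, the assessments are already scheduled, and the baseline visit (8.2.1) already scores before the eligibility decision. The downside is that a few poorly compliant subjects contribute Week 4 or Week 8 data and slightly dilute the estimate.
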